8.4.5 Physical examinations

Physical examination results will be presented in individual subject data listings.

8.4.6 Pregnancy Test

Pregnancy test results prior to treatment will be listed.

9. ANALYSES PERFORMED BEFORE DATABASE CLOSURE

No interim analyses are planned for this study.

10. CHANGES FROM METHODS PLANNED IN THE PROTOCOL

Any changes to methods planned in this SAP will be documented in a revision to this statistical plan prior to database lock, or identified in the clinical study report.

11. STATISTICAL SOFTWARE

The statistical software to be used for generation of the tables, listings, and figures is SAS[®] version 9.4.

12. REFERENCES

Not Applicable.

13. APPENDIX 1 DATA HANDLING RULES

Category	Description	Data Handling Rules
Demographics	Age at informed consent	Age = integer ([date of informed consent signed – date of birth + 1]/365.25) If in date of birth, only day is missing, it is imputed by 15th of the month of birth; both day and month are missing, it is imputed by July 1st of the year of birth.
Baseline		Baseline was defined as the last assessment made before the dose of the investigational product.
Vital Signs/ECG/Lab	Change from baseline	Change_t = Value_t - Value_{Baseline}

14. APPENDIX 2 SAS CODE FOR STATISTICAL ANALYSES

This section will be completed after examining the existing data and prior to the final signoff of this SAP.

Test	Table/Figure	SAS Codes for Modeling
ANOVA using a linear mixed-effects model.	PK endpoints requiring ANOVA.	
Analysis using PROC MIXED in SAS with SEQ, SUBJ, PERIOD, and TRTP identifying SEQUENCE, SUBJECT, PERIOD and TREATMENT variables. “Y” denotes the response measure (log (AUC), log (C_{MAX})). “KR” denotes Kenward-Roger method. “CL” denotes confidence limits.
 <pre> PROC MIXED METHOD=REML; CLASS SUBJ SEQ PERIOD TRTP; MODEL Y = SEQ PERIOD TRTP / DDFM=KR; RANDOM SUBJ(SEQ); LSMEANS TRTP / PDIF CL ALPHA = 0.10; ESTIMATE 'T/R' TREAT -1 1 / CL ALPHA = 0.1; RUN; </pre> 
Anti-log transformation to obtain the geometric means. “GEO” denotes geometric and “LS” denotes least square.
 <pre> DATA LSMEANS; SET LSMEAN GEOLSMEAN = EXP(ESTIMATE); RUN; </pre> 
Anti-log transformation to obtain the ratio of geometric means (point estimate) and 90% confidence interval (CI) – lower and upper bounds.
 <pre> DATA DIFFS; SET ESTIMATE; RATIO = EXP(ESTIMATE)*100; LOWER = EXP(LOWER)*100; UPPER = EXP(UPPER) * 100; RUN; </pre>

**15. APPENDIX 3 REFERENCE RANGES AND CLINICALLY RELEVANT CHANGES
FROM BASELINE FOR MARKED LABORATORY ABNORMALITIES**

<To be inserted>

16. APPENDIX 4 MOCKUP TABLES, LISTINGS, AND GRAPHS (TLGs)

Mockup tables, listings, and graphs are presented in a separate document.

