5.5 Blinding

This is an open-labeled study. There is no blinding process in this protocol.

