9 PLANNED STATISTICAL METHODS

9.1 General Considerations

The statistical evaluation of pharmacokinetic and pharmacodynamic parameters will be conducted by the designated CRO. A detailed Statistical and Analytical Plan will be generated prior to initiation of the study. Statistical analysis will be performed using Statistical Analysis Software SAS (SAS Institute Inc., USA). Non-compartmental analysis will be performed using Phoenix[®] WinNonlin[®] 6.4 (Certara, USA).

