1. INTRODUCTION

This Statistical Analysis Plan (SAP) outlines the statistical methods for the display, summary and analysis of data collected within the scope of Theracos Sub LLC protocol version 1.0 dated 19-Apr-2017. As with any SAP, the proposed methods and approaches to the data analysis should be deemed as flexible. The analysis of the data should allow changes in the plan to the extent that deviations from the original plan would provide a more reliable and valid analysis of the data. As such, the statistical analysis to a certain degree is iterative since much of the planning is based on assumptions that require verification. The purpose of this plan is to provide general guidelines from which the analysis will proceed. Nevertheless, deviations from these guidelines must be substantiated by a sound statistical rationale.

This SAP should be read in conjunction with the study protocol and the Case Report Forms (CRFs). This version of the SAP has been developed using the final version of the protocol mentioned above and the final version of the annotated CRFs dated 12-JUN-2017.

The SAP details the analysis of the data collected in the study and the presentation of the results of the analyses. The table, listing, and figure (TLF) shells are displayed in a companion document which provides information on the layout of the data displays.

All statistical analyses will be performed using SAS[®] version 9.4. Adverse events will be coded using the latest version of the Medical Dictionary for Regulatory Activities (MedDRA version 20.0 or newer).

This is a phase 1, single-center, open-label, randomized, two-period, two-treatment crossover study to assess the effects of exenatide injection on the pharmacokinetics (PK) and pharmacodynamics (PD) of bexagliflozin in healthy subjects. A total of 20 eligible healthy subjects will be enrolled and assigned to one of the two groups, with up to 10 subjects per group. Each group will receive both the treatments alternatively, in a crossover fashion (two-period, two-treatment crossover design) with the two treatment periods separated by a 7-day washout period.

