4. DATA AND ANALYTICAL QUALITY ASSURANCE

The overall quality assurance (QA) procedures for the study data, statistical programming and analyses are described in Everest's Standard Operating Procedures (SOPs). Detailed data management (DM) procedures are documented in the Data Management Plan, Data Validation Check Specifications, and Data Review Plan. Detailed statistical and programming quality control (QC) and QA procedures are documented in the Statistical Analysis and Programming QC/QA Plan.

The study endpoints and analytic approaches are both prospectively defined and documented in the protocol and in this SAP. The SAP will be finalized, and protocol violations will be identified and decisions for inclusion and exclusion of subjects from the PK and PD Populations will be made prior to the database lock and data analysis.

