The proportion of $AUC_{0-\infty}$ due to extrapolation (AUC_{extr}) will be calculated and expressed as a percentage. $AUC_{0-\infty}$ values will be considered unreliable estimates if the AUC_{extr} is greater than 20% and will be excluded from summary tables but will be listed.

CL/F will be calculated as $Dose/AUC_{0-\infty}$.

V_z/F will be calculated as $Dose/(\lambda_z \times AUC_{0-\infty})$.

$T_{1/2}$ will be calculated as $0.693/\lambda_z$.

Descriptive statistics for the plasma concentrations of bexagliflozin by Treatment and Timepoint will be provided. Listings of plasma concentrations by Subject Number, Treatment Sequence/Treatment, Period, and Timepoint will also be provided.

To assess the effect of co-administration of exenatide on the PK of bexagliflozin, an analyses of variance (ANOVA) using a linear mixed-effects model will be fitted to the natural logarithmic transformation of PK parameters of bexagliflozin (C_{max} , AUC_{0-t} and $AUC_{0-\infty}$). The linear mixed-effects model will include subject as a random effect, and treatment, period, and sequence as fixed effects. The 90% confidence intervals (CIs) will be constructed for the ratio of the least squares (LS) geometric means of PK parameters (C_{max} , AUC_{0-t} and $AUC_{0-\infty}$), when bexagliflozin is dosed in combination with exenatide versus when dosed alone, with 80-125% defined as the lack of interaction boundaries.

The ratios of geometric least squares means and corresponding 90% CI for the treatment comparison will be determined by exponentiating the mean differences between treatments on the logarithm scale. The intra-subject geometric CV%, $100\% * \sqrt{\exp(residual) - 1}$, where residual = the residual variance component and where exp is the natural exponential function, will be reported.

The appropriateness of the mixed model will be assessed through residual analyses. Any modifications required due to poor fit will be reported and executed.

Descriptive statistics for the PK parameters C_{max} , T_{max} , $AUC_{0-\infty}$, AUC_{0-t} , CL/F, V_z/F , λ_z , and $T_{1/2}$ will be tabulated by treatment. Means, standard deviations (SD), medians, ranges (minimum; maximum), and geometric means and coefficients of variation (CV) will be presented for all PK parameters with the exception of T_{max} . Medians and ranges will be presented for T_{max} .

A listing of derived PK parameters by Subject Number, Treatment Period, and Treatment will be provided.

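### The SAP leaves the PK model code to be completed after a look at the data and the poor-fit clause without a rule, in an open-label crossover whose main model is otherwise prespecified

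*SAP*

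**What the plan says.** - **SAP Appendix 2** prints PROC MIXED code and introduces it with: "This section will be completed after examining the existing data and prior to the final signoff of this SAP".
- **SAP 7.2** has the model's fit assessed from residuals and continues: "Any modifications required due to poor fit will be reported and executed". It names no criterion for poor fit and no alternative model, and does not say which fit is compared with 80-125%.
- **SAP section 1** says "the proposed methods and approaches to the data analysis should be deemed as flexible", but requires a sound statistical rationale for any deviation.
- **SAP section 4** says "The study endpoints and analytic approaches are both prospectively defined and documented in the protocol and in this SAP". It adds that finalisation of the SAP, identification of protocol violations and the decisions on the PK and PD populations "will be made prior to the database lock and data analysis".
- **Protocol 9.1**: "A detailed Statistical and Analytical Plan will be generated prior to initiation of the study".
- **Protocol 5.5**: "This is an open-labeled study. There is no blinding process in this protocol".

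The main model is the same in Protocol 9.5 and SAP 7.2: log Cmax, AUC0-t and AUC0-∞, subject random, treatment, period and sequence fixed, and a 90% confidence interval for the ratio judged against 80-125%. The printed code adds REML, Kenward-Roger degrees of freedom, subject nested in sequence, and alpha 0.10.

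**The concern.** Anyone who holds the concentrations and the treatment sequence in an unblinded two-period crossover can work out the treatment ratio. Code completed after such a look, together with an open licence to change the model for poor fit, leaves some of the analysis to be settled by someone who may already know on which side of the boundary the interval falls.

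The 80-125% comparison is how the PK part of the primary objective is judged. A 90% interval has its nominal coverage only if the model is chosen without regard to the result. Protocol 3.2 expects a small fall in Cmax with exenatide, so the lower limit is where a favourable choice of fit could matter.

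**Working it through.** **1. What is still open, from the text**

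| Item | Status |
|---|---|
| Endpoints, model terms, interval level, boundaries | Fixed in Protocol 9.5 and SAP 7.2 |
| REML, Kenward-Roger, alpha 0.10 | Printed in Appendix 2; alpha 0.10 matches the 90% interval |
| Treatment contrast | Not usable as printed: ESTIMATE names TREAT, while CLASS and MODEL name TRTP |
| Response to poor fit | Allowed in SAP 7.2, with no trigger, no fallback and no rule on which fit governs |
| Timing of code completion | After a look at undefined existing data (Appendix 2), against prospective definition and finalisation before lock (SAP 4) |

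So the code does need completing, at the line that produces the ratio and its interval. The room for a result-driven choice lies in that code and in the poor-fit clause.

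**2. How much the choice could matter**

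The plan has no figure to reproduce: it gives no within-subject CV, and the sample size has no formal basis.

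Inputs from the documents: 20 subjects, 10 per sequence; 90% interval; limits 0.80 and 1.25. Assumptions: within-subject CV of 15, 20 or 25%; true ratio 0.80 (exactly on the boundary); complete, log-normal data; no true period or sequence effect.

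- Within-subject SD on the log scale: σ = √ln(1 + CV²). This gives 0.149, 0.198 and 0.246 for CV 15, 20 and 25%.
- Each subject's log difference, combination minus alone, has SD √2·σ. At CV 20% this is 1.414 × 0.198 = 0.280.
- Estimate: the average of the two sequence means. SE = s_d/√20, with 18 degrees of freedom.
- Interval: exp(estimate ± 1.734 × SE), with t(0.95; 18) = 1.734. No interaction is concluded if the whole interval lies in 0.80-1.25.

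At a true ratio of 0.80 the lower limit clears 0.80 with probability P(t₁₈ > 1.734) = 5%. The upper limit hardly ever matters: at CV 20% the half-width is about 1.734 × 0.280/4.472 = 0.109 on the log scale, against a distance of 2 × 0.223 = 0.446 between the limits.

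Simulation of 40,000 trials per CV, counting a conclusion of no interaction if **either** the fixed model **or** the stated alternative gives it:

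| Choice available | Wrong conclusion of no interaction |
|---|---|
| Fixed 7.2 model only | 5.0-5.2% |
| Or period and sequence dropped | 5.2-5.5% |
| Or one subject removed if studentized residual > 3 | 5.2-5.4% |
| Or one subject removed if studentized residual > 2.5 | 6.5-6.6% |
| Or largest-residual subject always removable | 10.3-10.5% |
| All of: fixed model, terms dropped, largest residual always removable | 10.4-10.6% |

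The residuals are internally studentized. An externally studentized cut-off of 3 corresponds to an internal one of 3 × √(18/(17 + 9)) = 2.50, so it belongs with the 6.5-6.6% row. Looser cut-offs lie between that row and the roughly 10% row.

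Nearly all of the last two rows comes from removing one subject from well-behaved data. Dropping model terms adds only about 0.2-0.3 points to the fixed model.

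**The case against.** The strongest reply is that the primary analysis is already fixed in the protocol and again in SAP 7.2, and that Appendix 2 is largely written. On this view its opening sentence is about finishing code, not choosing a model. The SAP also has safeguards: deviations need a sound rationale (section 1), modifications are reported (7.2), and changes go into a SAP revision before database lock or are identified in the study report (section 10). All of this stands and limits the point. It does not say when the code is fixed relative to sight of the data, or which fit carries the conclusion. SAP section 10 also allows a change to appear only in the study report.

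Four stronger readings are tempting, and the documents do not support them:

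- **That the primary model is open.** It is not; its terms, interval and boundaries are prespecified.
- **That the protocol's timing was breached.** Protocol 9.1 has the plan generated, not finalised, before initiation. The text available gives neither the SAP signoff date nor the first dosing date. Existing data is undefined and might mean dataset structure or variable names, though the SAP does not say so.
- **That subjects may be deleted as outliers.** SAP 7.2 speaks of modifying the model; no passage provides for removing a subject because of a large residual.
- **That the error rate doubles to about 10%.** That needs unconditional freedom to delete one subject, with the favourable fit always chosen. It is a worst case, not what the text allows.

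SAP 3.3 also plans no formal hypothesis testing. The 80-125% comparison is still a decision rule, but the harm is better described as possible bias in an interval-based conclusion than as loss of a stated type I error.

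**Conclusion.** The point holds as a conflict between stated plans and a gap in SAP 7.2. Appendix 2 puts code completion after a data look in an unblinded study, which does not fit SAP section 4 and sits awkwardly with Protocol 9.1. The poor-fit clause lacks a trigger, a fallback and a governing fit.

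The likely size is small. Under the assumptions above, the chance of wrongly concluding no interaction at a true ratio of 0.80 moves from about 5% to between 5.2% and 6.6% for the dropped-terms and residual cut-off options examined. About 10% marks only the extreme. These figures rest on an assumed CV of 15-25% and illustrate possible choices; they do not estimate what the analysts would do. This is a cheap improvement, not a flaw that undermines the study.

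**What to change.** 1. In SAP Appendix 2, remove the clause that places completion after a look at the data. If it meant only checking variable names or dataset structure, say that and exclude post-dose results.
2. Correct the ESTIMATE line to name TRTP, as CLASS and MODEL do, and check that its sign gives combination over alone. Locking the code as printed would not produce the contrast.
3. State that the code is signed off before any bexagliflozin concentration is released to the statistician.
4. In SAP 7.2, state that the specified model is the basis of the 80-125% conclusion and that any refit for poor fit is reported beside it as a sensitivity analysis. Naming a fallback model and its trigger in advance would also close the gap, but is more to write.

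The cost is SAP wording and one line of code, with no new data, subjects or procedures. The downside is that a model with imperfect fit stays primary; showing the refit beside it lets the reader judge whether that matters.
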